10.5.2 Analysis Plan

For the interim PK assessment in Arm 1 participants, PK data from the SPRING-1 study [15] will form the basis of the opening rule for Arm 2. Refer to [section 7.4](#) for criteria and considerations for opening Arm 2.

10.6 Analyses

Primary outcome plasma PK parameters (C_{min} , AUC_{0-24h} , and C_{max}) will be determined using **nonlinear mixed-effects population pharmacokinetic modeling**. PK parameters will be log-transformed as needed.

Primary PK analysis:

The bootstrap method with replacement will be applied on the observed C_{trough} values from Arm 1, and the mean and 95% CI of the 5th percentile C_{trough} will be calculated. The **lower bound of a 95% CI around the 5th percentile of C_{min}** from Arm 1 will be compared with the 5th percentile of C_{tau} in the DTG 10 mg dosing arm (i.e., 158 ng/mL) from the SPRING-1 study, which has been demonstrated to be sufficient in maintaining viral suppression. If the **lower bound of the 95% CI around the 5th percentile C_{min}** is greater than 158 ng/mL, the dosing is considered acceptable. The same analysis will be conducted for Arm 2 if it opens.

Geometric mean ratios and associated 90% confidence intervals within arm will be calculated to assess the overall effect of 1HP on DTG PK.

For all PK parameters (including both primary and other outcome PK measures), descriptive statistics including mean, standard deviation, median, interquartile range, minimum, and maximum will be presented. All statistical tests will be performed without adjustment for multiple comparisons unless otherwise stated.

Detailed analysis methods will be put in a Statistical Analysis Plan.

Because PK variability has been associated with differences in drug response, understanding whether differences in DTG and RPT concentrations observed in A5372 have a genetic basis will be explored as an exploratory objective. Polymorphisms in host genes involved in both DTG and RPT metabolism or transport will be explored. The primary genes of interest will include: CYP3A4/5, UGT1A1, PXR (pregnane x receptor), CAR (constitutive androstane receptor), as well as other metabolic enzymes and transporters that may play a role in either DTG or RPT disposition (TBD).

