2.2 Hypothesis

Dolutegravir (DTG) concentrations, when given twice daily (BID) or once daily (QD) with coadministration of 4 weeks daily rifapentine (RPT) (600 mg) and isoniazid (INH) (300 mg) [1HP], will maintain steady-state plasma trough DTG concentrations above 158 ng/mL in 95% of study participants. The value 158 ng/mL is the 5th percentile steady-state trough concentrations of DTG which has been demonstrated to be sufficient in maintaining virologic suppression.

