4.5.2 Model-based Interim Analysis (Conducted by Study Pharmacologist)

Criterion for opening Arm 2. In addition to the three criteria above, when DTG concentrations from at least 32 evaluable participants (ie, participants in the primary PK analysis population) in Arm 1 are available, a model-based evaluation of DTG PK in these BID participants will occur. The study pharmacologist will develop a nonlinear mixed-effects population pharmacokinetic model, based on available concentrations from all Arm 1 participants (ie, participants in the secondary PK analysis population). From the developed and evaluated model, concentrations for 100 hypothetical participants will be simulated for Arm 2/QD dosing of DTG 1000 times. The parameter of primary interest is C_{24} , the expected DTG concentration at the end of the 24h dosing interval at steady state. For each simulated trial, the 5th, 50th, and 95th percentile of DTG trough concentrations, C_{24} , will be determined.

Of the 1000 simulated trials, the median value of the 5th percentile of DTG C_{24} will be compared to 158 ng/mL, which is the 5th percentile of DTG C_{24} observed for the 10 mg daily DTG dose in SPRING-1. If the median C_{24} value among simulated 5th percentiles is at or above 158 ng/mL, A5372 Arm 2 will open for enrollment, for evaluation of DTG 50 mg QD dosing with 1HP.

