4.6 Analysis of the Primary Objective 1 (Conducted by Study Pharmacologist)

In order to determine the dosing for DTG that, when given together with 1HP, achieves target exposures (C_{24}) of standard-dose DTG when it is given without RPT, the distribution of simulated DTG C_{24} values (based on concentrations from Arm 1 and develop population pharmacokinetic model) will be compared

with the historical data from SPRING Study (e.g., C_{tau} in the DTG 10 mg dosing arm) to examine whether dosing of DTG 50 mg BID will maintain above the trough concentration necessary for virologic suppression.

The same analysis will be conducted for Arm 2 if it opens. For this objective, a separate population PK analysis will be conducted (as described in Section 4.5.2).

There is no specific outcome measure associated with this analysis. The “outcome” is the characterization (through modeling) of the relationship between dosing (amounts, frequencies) and CIs around predicted C_{min} values; this analysis will be performed by the study pharmacologist.

4.7 Analysis of Primary Objectives 2 and 3 (outcome measures listed in Section 3.1; conducted by Study Pharmacologist)

For all PK parameters, the following descriptive statistics will be reported by arm and visit: mean, standard deviation, coefficient of variation, median, 5th and 95th percentiles, minimum, and maximum, as well as mean and standard deviation on the natural log (base e) scale. This analysis is conducted using the primary PK analysis population. To assess the overall effect of 1HP on DTG PK parameters, geometric mean ratios (GMRs) and associated 90% CIs will be calculated by arm. The ratio is with (after initiation of 1HP; numerator) vs without (before initiation of 1HP; denominator) co-administered 1HP. The DTG PK parameters are C_{min} , C_{max} , and total daily exposure as measured by AUC_{0-24h} . (For Arm 1, day 28 (BID dosing), participant-specific AUC_{0-24h} will be estimated by combining (summing) areas for the two BID dosing intervals. For Arm 1 day 0, and for Arm 2 days 0 and 28 (QD dosing), participant-specific AUC_{0-24h} values will be estimated from concentrations collected over the single 24-hour dosing interval.)

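### Protocol 10.6 and SAP 4.6 address Primary Objective 1 by different, unreconciled analyses, and the 10.6 bootstrap limit, read in the usual way, gives 80.6% to 84.2% one-sided confidence, not 97.5%

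*Protocol*

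**What the plan says.** Under its primary PK analysis, Protocol 10.6 says: "The bootstrap method with replacement will be applied on the observed C_{trough} values from Arm 1". If the lower bound of the 95% CI around the 5th percentile "is greater than 158 ng/mL, the dosing is considered acceptable". The same analysis applies to Arm 2 if that arm opens. The bootstrap sentence refers to C_trough, while the decision sentences refer to C_min. Neither the type of bootstrap interval nor the quantile definition is given. The section adds: "Detailed analysis methods will be put in a Statistical Analysis Plan".

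SAP 4.6 is the section on Primary Objective 1. It compares the distribution of simulated C24 from a population PK model with the SPRING-1 10 mg data, "to examine whether dosing of DTG 50 mg BID will maintain above the trough concentration necessary for virologic suppression". It describes its result as a modelled relationship between dosing and CIs around predicted C_min, and states: "There is no specific outcome measure associated with this analysis". For the modelling it refers to SAP 4.5.2. The cut-off there (median simulated 5th percentile at or above 158 ng/mL) is written as the condition under which "A5372 Arm 2 will open for enrollment, for evaluation of DTG 50 mg QD dosing with 1HP".

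Protocol 10.2.1.2 lists Day 28 C_trough as a primary outcome. SAP 3.1 carries only 10.2.1.1. SAP 5.8 lists descriptive summaries and geometric mean ratios. SAP 4.3 gives every CI other than those for geometric mean ratios 95% coverage.

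**The concern.** The hypothesis in SAP 2.2 is that dosing with 1HP "will maintain steady-state plasma trough DTG concentrations above 158 ng/mL in 95% of study participants". Only an analysis of the lower tail of the trough distribution can answer that; a geometric mean ratio cannot. The plan offers two such analyses, which differ in data (observed or simulated), in statistic (bootstrap lower bound or comparison of distributions) and in rule (explicit or none). If they disagree, nothing in the plan says which prevails, and the choice could be made after the results are known.

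The second worry is that a nonparametric bootstrap of a 5th percentile has very little to resample at this size: 5% of 32 is 1.6 participants. The lower limit may then not carry the confidence that a 95% label promises, and that limit is what declares the dosing acceptable.

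**Working it through.** **Inputs**
- Evaluable n per arm: 32 (protocol schema). Enrolled n per arm: 36 (Protocol 10.4). Check: 36/32 = 1.125, which agrees with the stated increase of about 12%.
- Quantile of interest: the 5th percentile. Target: 158 ng/mL (Protocol 10.6).
- Level: 95% CI. Sidedness is not stated. Taken as two-sided and equal-tailed, it puts 2.5% below the lower limit, so the lower bound is nominally a 97.5% one-sided limit.
- Assumptions: one independent trough per participant, a continuous distribution, and a percentile interval.

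**Step 1. Which value is the percentile-bootstrap lower limit?**
At n=32 to 36 the usual definitions place the sample 5th percentile between ordered positions 1.6 and 2.75. It therefore depends on at most the third smallest value. If a resample contains the sample minimum three or more times, its 5th percentile equals that minimum. The number of copies is binomial(n, 1/n):
- n=32: 1 - (0.3621 + 0.3737 + 0.1869) = 0.0773
- n=36: 1 - (0.3627 + 0.3731 + 0.1865) = 0.0777

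Under the inverse-CDF definition two copies suffice, with probability 0.264. All of these exceed 0.025, and no resample can go below the minimum, so the lower limit is the sample minimum. Simulation agreed: the two coincided in every trial.

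**Step 2. What confidence does the sample minimum carry?**
The minimum lies at or below the true 5th percentile unless all n values lie above it:
- n=32: 1 - 0.95^32 = 1 - 0.1937 = 80.6%
- n=36: 1 - 0.95^36 = 1 - 0.1578 = 84.2%

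For the minimum to be a valid limit, n must be at least ln(0.025)/ln(0.95) = 71.9, so 72, for 97.5% one-sided confidence; or ln(0.05)/ln(0.95) = 58.4, so 59, for 95%.

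**Step 3. How does the acceptance rule behave?**
The rule accepts when every observed trough exceeds 158 ng/mL. If a share p of the population lies below 158, the acceptance probability is (1-p)^n:

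| True share below 158 ng/mL | n=32 | n=36 |
|---|---|---|
| 2% | 52.4% | 48.3% |
| 5% | 19.4% | 15.8% |
| 10% | 3.4% | 2.3% |

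At the 5% boundary a genuine 97.5% limit would accept 2.5% of the time.

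**Step 4. Would another bootstrap interval repair it?**
In simulation (log-normal troughs, CV 30% and 71%, three quantile definitions, 600 trials each) BCa gave the same coverage as the percentile interval. Basic and normal-approximation intervals covered about 85% to 97%, depending on CV and quantile definition. None reached 97.5%.

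**Step 5. Is the rule settled elsewhere in the SAP?**
No. SAP 4.6 states no pass value and no role for its CIs. SAP 4.8.1 leaves the Objective 1 estimand undefined. SAP 2.1 bases final inference on geometric mean ratios. SAP 4.7 reports the 5th percentile and minimum of C_min, but only descriptively. SAP 4.4 gives C_min both a model-based and an observed version, so the C_trough/C_min mix in Protocol 10.6 stays open. An observed C_min cannot exceed the trough of the same interval, so that mix leans conservative, but it is undefined.

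**The case against.** Four points on the other side deserve weight.

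First, the protocol leaves detailed methods to the SAP, so SAP 4.6 might be taken to govern. But a detailed method would elaborate the bootstrap or withdraw it, and the SAP does neither.

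Second, a reader might infer that the SAP ignores uncertainty, or that it accepts a regimen whenever the simulated median 5th percentile reaches 158 ng/mL, and so is systematically more lenient than the protocol. The documents do not support that. SAP 4.6 mentions CIs around predicted C_min, and the 4.5.2 cut-off is written for opening Arm 2 only. Comparing a lower confidence limit with 158 ng/mL, in place of a point estimate, changes both the size and the main direction of any disagreement with the bootstrap. A rate of conflicting verdicts therefore cannot be derived from the plan.

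Third, a reader might fault Protocol 10.6 for rejecting 81% to 84% of trials of a regimen that exactly matches the 10 mg distribution. That is not a defect. Such a regimen sits on the boundary, where a valid 97.5% limit would reject 97.5%. A lenient opening gate followed by a stricter final criterion is ordinary staging.

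Fourth, 80.6% and 84.2% rest on choices that the protocol does not state. Protocol 7.4 calls both the 23- and 24-hour samples trough, and pooling them would change the figures and introduce clustering. Because the decision sentences concern C_min, which 10.6 says is determined by population modelling, a model-based interval is also a possible reading. This stands, and it is why the coverage result is conditional. The practical reach may also be narrow for Arm 1. Protocol 2.1.1 reports a median C12 of 1,123 ng/mL for twice-daily DTG with rifampin, about seven times 158 (1,123/158 = 7.1). If rifapentine behaved similarly, which is an assumption, both routes would probably accept.

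**Conclusion.** The point holds in two parts, and I rate it should-fix. First, two unreconciled analyses address Primary Objective 1: one has an explicit rule and the other has none, and outcome 10.2.1.2 is missing from the SAP's lists. They can give different verdicts; how often, and in which direction, depends on a decision step that the SAP does not state. Protocol 10.6 does not name Objective 1, but its acceptability rule is the only one in either document that answers it for the final analysis.

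Second, if the bootstrap governs with an equal-tailed percentile or BCa interval and one trough per participant, the lower bound falls 16.9 percentage points (n=32) or 13.3 points (n=36) short of 97.5% one-sided confidence. False acceptance at the boundary is then 19.4% or 15.8%, where 2.5% is implied. The 2.5% is inferred from a two-sided 95% CI; no document states an error rate. The percentile figures do not depend on the shape of the trough distribution, provided it is continuous. The rule is not lax throughout: it seldom accepts a regimen with 10% below target and rejects about half of trials with 2% below.

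**What to change.** State in both Protocol 10.6 and SAP 4.6 which analysis decides acceptability in each arm. Base it on one named Day 28 variable with one value per participant, and carry 10.2.1.2 into SAP 3.1 and 5.8.

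- If the bootstrap is kept, name the interval type and quantile definition, and report the one-sided confidence achieved (80.6% at n=32, 84.2% at n=36 for the percentile limit) in place of 95%.
- If the model decides, state that the lower limit of the 95% CI for the model-based 5th percentile is what is compared with the plan's existing 158 ng/mL target.

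Both options are changes of wording and need no new participants or samples. The first means stating openly a lower confidence than the plan now advertises. The second sets a stricter hurdle than comparing a point estimate, so an adequate regimen would be somewhat less likely to pass.

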11.0 PHARMACOLOGY PLAN

See [section 6.3.11](#) for details on PK sampling and [section 10.6](#) for details of population PK modeling.

12.0 DATA COLLECTION AND MONITORING

12.1 Records to Be Kept

Electronic case report form (eCRF) screens will be made available to sites for data entry. Participants must not be identified by name on any data submitted to the DMC.

Participants will be identified by the patient identification number (PID) and study identification number (SID) provided by the ACTG DMC upon registration.

12.2 Role of Data Management

- 12.2.1 Instructions concerning entering study data on eCRFs will be provided by the ACTG DMC. Each CRS is responsible for keying the data in a timely fashion.
- 12.2.2 It is the responsibility of the ACTG DMC to assure the quality of computerized data for each ACTG study. This role extends from protocol development to generation of the final study databases.

12.3 Clinical Site Monitoring and Record Availability

- 12.3.1 Site monitors under contract to the NIAID will visit participating clinical research sites to review the individual participant records, including consent forms, eCRFs, supporting data, laboratory specimen records, and medical records (physicians' progress notes, nurses' notes, individuals' hospital charts), to ensure protection of study participants, compliance with the protocol, and accuracy and completeness of records. The monitors also will inspect sites' regulatory files to ensure that regulatory requirements are being followed and sites' pharmacies to review product storage and management.

Monitoring visits may be conducted on-site or remotely. Remote visits may include remote source document verification using methods specified for this purpose by NIAID. Remote monitoring visits may be performed in place of, or in addition to onsite visits to ensure the safety of study participants and data integrity [23]. The site will make available study documents for site monitors to review utilizing a secure platform that is HIPAA and 21 CFR Part 11 compliant. Potential platform options include: Veeva SiteVault, site-controlled SharePoint or cloud-based portal, direct access to Electronic Medical Record (EMR), and Medidata Rave Imaging Solution. Other secure platforms that are 21 CFR Part 11 compliant may be utilized, as allowed by the DAIDS Office of Clinical Site Oversight (OCSO).

- 12.3.2 The site investigator will make study documents (e.g., consent forms, drug distribution forms, eCRFs) and pertinent hospital or clinic records readily available for inspection by the local IRB/EC, the site monitors, the ACTG, the FDA, the NIAID, the OHRP, the industry supporter(s) or designee, and other local, US, and international regulatory entities for confirmation of the study data.

13.0 PARTICIPANTS

13.1 Institutional Review Board (IRB) Review and Informed Consent

This protocol and the informed consent document ([Appendix II](#)) and any subsequent modifications will be reviewed and approved by the IRB or EC responsible for oversight

of the study. A signed consent form will be obtained from the participant (or legal guardian, or person with power of attorney for participants who cannot consent for themselves). The consent form will describe the purpose of the study, the procedures to be followed, and the risks and benefits of participation. A copy of the consent form will be given to the participant, or legal guardian, and this fact will be documented in the participant's record.

13.2 Participant Confidentiality

All laboratory specimens, evaluation forms, reports, and other records that leave the site will be identified by coded number only to maintain participant confidentiality. All records will be kept locked. All computer entry and networking programs will be done with coded numbers only. Clinical information will not be released without written permission of the participant, except as necessary for monitoring by the ACTG, IRB/EC, FDA, NIAID, OHRP, or other local, US, and international regulatory entities as part of their duties.

13.3 Study Discontinuation

The study may be discontinued at any time by the ACTG, IRB/EC, FDA, NIAID, OHRP, or other local, US, and international regulatory entities as part of their duties to ensure that research participants are protected.

14.0 PUBLICATION OF RESEARCH FINDINGS

Publication of the results of this trial will be governed by ACTG policies.

15.0 BIOHAZARD CONTAINMENT

As the transmission of HIV and other blood-borne pathogens can occur through contact with contaminated needles, blood, and blood products, appropriate blood and secretion precautions will be employed by all personnel in the drawing of blood and shipping and handling of all specimens for this study, as currently recommended by the CDC and the National Institutes of Health.

All dangerous goods and materials, including diagnostic specimens and infectious substances, must be transported using packaging mandated by CFR 42 Part 72. Please refer to instructions detailed in the International Air Transport Association (IATA) Dangerous Goods Regulations.

APPENDIX I: PROHIBITED AND PRECAUTIONARY MEDICATIONS

Division of AIDS
AIDS CLINICAL TRIALS GROUP (ACTG)
For Protocol A5372

The prohibited and precautionary medications with dolutegravir (DTG), rifapentine (RPT), and isoniazid (INH) are listed below.

I. Prohibited Medications

- Phenytoin
- Phosphenytoin
- Lamotrigine
- Perampanel
- Phenobarbital
- Primidone
- Carbemazepine
- Oxcarbazepine
- Eslicarbazepine
- Felbamate
- St. John's wort
- Dofetilide
- Azole antifungals including fluconazole, itraconazole, ketoconazole and posaconazole (topical formulations are acceptable as they do not achieve systemic concentration)
- Enzalutamide
- Mitotane
- Other rifamycin antibiotics including rifabutin and rifampicin
- Tenofovir alafenamide (TAF)
- Other antiretroviral drugs except DTG and 2 NRTI
- Protease inhibitors (HIV or HCV)

II. Precautionary Medications

- Antacids – follow product labeling for instructions on separation with DTG
- Buffered Medications – follow product labeling for instructions on separation with DTG
- Divalent cations (e.g., calcium or iron supplements) – follow product labeling for instructions on separation with DTG
- Ethinyl estradiol/norgestimate
- Metformin
- Methadone
- Multivitamin – follow product labeling for instructions on separation with DTG
- Omeprazole
- Prucalopride
- Sucralfate
- Topiramate

1.1 Purpose

This Primary Statistical Analysis Plan (SAP) describes the primary, secondary, and selected exploratory outcome measures of the A5372 study that will be included in the primary manuscript addressing the major primary and secondary objectives of the study, as well as the primary and secondary outcome measures for which results will be posted on ClinicalTrials.gov. The Primary SAP also outlines the general statistical approaches that will be used in the analysis of the study. It has been developed to facilitate discussion of the statistical analysis components among the study team, and to provide agreement between the study team and statisticians regarding the statistical analyses to be performed and presented in the primary statistical analysis report.

1.2 Version History

Version	Changes Made	Rationale	Effective Date
1.0	Original Version (For protocol version 2.0. Note that the original SAP was still in draft form when participants began enrolling under protocol version 1.0; no final version of the SAP was filed that corresponds to protocol version 1.0. Issue Tracking ID 40443 [deviation].)	N/A	7/7/2021

1.3 Abbreviations

Abbreviation	Full text
1HP	4-week (1 month) daily regimen of isoniazid and rifapentine
ART	Antiretroviral therapy
ARV	Antiretroviral (drug)
AUC	Area under the concentration-time curve
BID	Twice daily
C _{max}	Maximum concentration observed over the dosing interval
C _{min}	Minimum concentration observed over the dosing interval
DTG	Dolutegravir; may refer to antiretroviral drug administered as part of an ARV regimen, or to concentrations of the drug as measured in plasma by pharmacology assay
H	One-letter abbreviation for isoniazid, used in the one-letter-per-drug notation for TB regimens
HIV-1	Human immunodeficiency virus, type 1 (the predominate type world-wide)
INH	Isoniazid
LTBI	Latent TB infection
NRTI	Nucleoside reverse transcriptase inhibitor
P	One-letter abbreviation for rifapentine, used in the one-letter-per-drug notation for TB regimens
PK	Pharmacokinetic

PWH	People with HIV
QD	Once daily
RPT	Rifapentine

2 Study overview

